7.4. NON-CLINICAL CRITERIA:**• Withdrawal of participation from study observation period**

Patients may withdraw their consent to participate in the study observation period at any time. If the patient wishes to remain in the clinical study, the follow-up period will immediately begin at the termination of study observation period. All data will continue to be collected per protocol.

The Principal Investigator will notify the Sponsor's Chief Medical Officer or designee within 24 hours of withdrawal of participation.

- **Withdrawal of consent**

If a patient or legal representative withdraws consent, all protocol related activities will be immediately discontinued. If study therapy (CRRT+SCD) is being administered at the time of withdrawal, normal procedures will be followed for CRRT+SCD therapy discontinuation (please see SCD Operator's Manual). No further study activity will be conducted.

The Principal Investigator will notify the Sponsor's Chief Medical Officer or designee within 24 hours of withdrawal of consent.

8. CLINICAL TRIAL TERMINATION CRITERIA

The Sponsor reserves the right to terminate the clinical trial for safety or administrative reasons at any time. If the Sponsor, Principal Investigator, Data Safety Monitoring Board (DSMB), Institutional Review Board (IRB), or Food and Drug Administration (FDA) officials discover conditions during the study indicating that the trial or participation by a clinical site should be discontinued, this action may be taken after appropriate consultation between the Sponsor and the Investigators.

Conditions that may warrant discontinuation of the trial at a specific clinical site may include the following:

- Failure of the Investigator to enroll patients into the trial at an acceptable rate (as defined and agreed upon between the Investigator and the Sponsor).
- Failure of the Investigator to comply with the pertinent FDA regulations.
- Submission of false information by the Investigator from the research facility to the Sponsor or the FDA.
- Failure to achieve and maintain post filter iCa levels of <0.40 mmol/L

Conditions that may warrant discontinuation of the trial may include, but are not limited to, the following:

- Discovery of an unexpected, serious or unacceptable risk to the patients enrolled in the study.
- Decision on the part of the Sponsor to suspend or discontinue testing, evaluation or development of the study product at any time.

9. SAFETY

9.1. ADVERSE EVENTS

An Adverse Event is any sign, symptom, illness, clinically significant abnormal laboratory value or other adverse medical event that appears for the first time or worsens in a subject (control or treatment arm) during this clinical study, regardless of whether or not it is considered related to the device.

- Blood and lymphatic system disorders (e.g., anemia, disseminated intravascular coagulation (DIC), heparin-induced thrombocytopenia (HIT), hypercoagulation, leukocytosis, thrombocytopenia, and thrombocytosis);
- Cardiac disorders (e.g., atrial fibrillation, atrial flutter, bradycardia, cardiogenic shock, non-ST segment elevation myocardial infarction, sinus tachycardia, ventricular fibrillation, and ventricular tachycardia);
- Gastrointestinal disorders (i.e., blood in stool, constipation, distended abdomen, gastrointestinal bleeding, ileus, nausea, pancreatitis, vomiting)
- General disorders and administration site conditions (i.e., chest pain, generalized aching, high temperature, hypothermia, multi-organ failure)
- Infections and infestations (i.e., candidiasis, gangrene, klebsiella pneumonia infection, methicillin-resistant staphylococcus aureus (MRSA) infection, pneumonia, sepsis, septic shock, and urinary tract infection (UTI));
- Injury, poisoning and procedural complications (e.g., post procedural pain);
- Metabolism and nutrition disorders (i.e., hypercalcemia, hyperglycemia, hyperkalemia, hypernatremia, hypervolemia, hypocalcemia, hypoglycemia, hypokalemia, hypomagnesemia, hyponatremia, hypophosphatemia, malnutrition, metabolic acidosis, and metabolic alkalosis);
- Musculoskeletal and connective tissue disorders (e.g., muscle spasm);
- Nervous System Disorders (e.g., encephalopathy, mental deterioration, stroke);
- Psychiatric disorders (e.g., agitation, anxiety, confusion, insomnia, mental status changes);
- Renal and urinary disorders (e.g., acute retention of urine, renal failure);
- Respiratory, thoracic and mediastinal disorders (e.g., acute respiratory failure, aspiration pneumonia, atelectasis, hypoxemia, pleural effusion, pneumothorax, pulmonary thromboembolism, respiratory failure, and thoracic hemorrhage);
- Skin and subcutaneous tissue disorders (e.g., macular rash, skin ulcer); and
- Vascular disorders (e.g., deep vein thrombosis, hypertension, hypotension, and jugular vein thrombosis).

9.2. SERIOUS ADVERSE EVENTS

Any Adverse Event, whether considered study-treatment related or not, which fits any of the criteria below, is considered a serious adverse event (SAE):

- Results in death
- Is life-threatening (meaning that the patient was at risk of death at the time of the event; this does not refer to an event which might have caused death if it had occurred in a more severe form)
- Requires in-patient hospitalization or prolongs the existing hospitalization
- Is a persistent disability/incapacity
- Is a congenital anomaly or birth defect
- Is considered an important medical event by the Principal Investigator (e.g., surgery, return to ICU, emergency procedures)

9.3. UNANTICIPATED ADVERSE DEVICE EFFECT

Unanticipated adverse device effect (UADE) is any serious adverse effect on health or safety, any life-threatening problem or death caused by, or associated with a device, if that effect, problem, or death was not previously identified in nature, severity, or degree of incidence in the application; or any other unanticipated serious problem associated with a device that relates to the rights, safety, or welfare of subjects. UADEs are reported to FDA as they occur (e.g., no later than 10 working days after CytoPherx first receives notice of the effect), as mandated by 21 CFR 812.150(b)(1).

9.4. ANTICIPATED ADVERSE EVENT

Co-morbidities and symptoms/laboratory/physiological deviations normally associated with pre-existing conditions (e.g., diabetes, ASHD, other C-V conditions, pneumonia, dialysis shunt problems, neurologic deficits) are considered “anticipated adverse reactions.” The investigator is required to take special care in differentiating concomitant illness events from those related to the therapy by use of patient history, relationship to treatment time and cartridge integrity, and other characteristics of clinical circumstances present at the time of the adverse experience, including drug interactions of concomitant medications and effects of surgical and/or medical procedures.

Adverse events associated with CRRT or underlying critical illness are also to be considered “anticipated”. Such events include, but are not limited to: thrombocytopenia, hyponatremia, hypokalemia, hypo- or hypercalcemia, hypo- or hyperglycemia, air embolism, hypotension, hemolysis, increased oxygenation requirements, leukopenia, arrhythmias, hypothermia, lactic acidosis, temporary decrease in cardiac output or cardiac index, disruption of skin integrity, bleeding, shock, bacteremia, hypotension, seizure, and death.

In addition, the following adverse events were experienced in the SCD-003 clinical trial and are considered anticipated:

- Blood and lymphatic system disorders (i.e., Anemia, Disseminated intravascular coagulation (DIC), Heparin-induced thrombocytopenia (HIT), Hypercoagulation, Leukocytosis, Thrombocytopenia, Thrombocytosis)
- Cardiac disorders (i.e., Atrial fibrillation, Atrial flutter, Bradycardia, Cardiogenic shock, Non ST segment elevation myocardial infarction, Sinus tachycardia, Ventricular fibrillation, Ventricular tachycardia)
- Gastrointestinal disorders (i.e., Blood in stool, Constipation, Distended abdomen, Gastrointestinal bleeding, Ileus, Nausea, Pancreatitis, Vomiting)
- General disorders and administration site conditions (i.e., Chest pain, Generalized aching, High temperature, Hypothermia, Multi organ failure)
- Infections and infestations (i.e., Candidiasis, Gangrene, Infection Klebsiella pneumonia, Infection MRSA, Pneumonia, Sepsis, Septic shock, UTI)
- Injury, poisoning and procedural complications (i.e., Post procedural pain)
- Metabolism and nutrition disorders (i.e., Hypercalcemia, Hyperglycemia, Hyperkalemia, Hypernatremia, Hypervolemia, Hypocalcemia, Hypoglycemia, Hypokalemia, Hypomagnesemia, Hyponatremia, Hypophosphatemia, Malnutrition, Metabolic acidosis, Metabolic alkalosis)
- Musculoskeletal and connective tissue disorders (i.e., Muscle spasm)
- Nervous system disorders (i.e., Encephalopathy, Mental deterioration, stroke)
- Psychiatric disorders (i.e., Agitation, Anxiety, Confusion, Insomnia, Mental status changes)
- Renal and urinary disorders (i.e., Acute retention of urine, Renal failure)
- Respiratory, thoracic and mediastinal disorders (i.e., Acute respiratory failure, Aspiration pneumonia, Atelectasis, Hypoxemia Pleural effusion, Pneumothorax, Pulmonary thromboembolism, Respiratory failure, Thoracic hemorrhage)
- Skin and subcutaneous tissue disorders (i.e., Macular rash, Skin ulcer)
- Vascular disorders (i.e., Deep vein thrombosis, Hypertension, Hypotension, Jugular vein thrombosis).

Any questions as to the expectedness of an adverse event will be discussed with CytoPherx's CMO and/or the DSMB.

9.5. CAUSALITY

All enrolled patients must have all AEs assessed for causality (probability that the AE may have been caused by the study treatment) by the Principal Investigator. The following definitions for causality assessment will be used in this study:

9.5.1. DEFINITELY RELATED

A clinical event, including a significant change in a laboratory test, that occurs in a plausible time relationship to the SCD treatment or other protocol-required activity, and which cannot be explained by concurrent disease or other drugs, chemicals, or procedures and that follows a clinically reasonable response upon withdrawal of the SCD treatment.

9.5.2. PROBABLY RELATED

A clinical event, including a significant change in a laboratory test, that occurs within a reasonable time sequence in relationship to the SCD treatment or other protocol-required activity that is unlikely to be attributed to concurrent disease, other drugs, chemicals, or procedures, and that follows a clinically reasonable response upon withdrawal of the SCD treatment.

9.5.3. POSSIBLY RELATED

A clinical event, including a significant change in a laboratory test, that occurs within a reasonable time sequence in relationship to the SCD treatment or other protocol-related activity that could also be explained by concurrent disease, drugs, chemicals, or procedures. The clinical course after withdrawal of the SCD treatment may be unclear with respect to the contribution of the SCD treatment to the AE.

9.5.4. UNRELATED

An AE, including a significant change in a laboratory test, that occurs with a temporal relationship to the SCD treatment or protocol-required activity that makes an association with the SCD treatment or study activity improbable, and in which other drugs, procedures or underlying disease(s) provide likely explanation.

9.6. SEVERITY – INTENSITY

The intensity of all adverse events should be evaluated using the following definitions:

9.6.1. MILD

An event that requires minimal clinical treatment or an adverse event requiring monitoring but no intervention or treatment; causes slight discomfort.

9.6.2. MODERATE

An event that requires non-routine intervention, (i.e., a new clinical treatment or diagnostic procedure), administered within an hour of the event; causes annoying discomfort.

9.6.3. SEVERE

An event requiring immediate intervention; causes significant discomfort.

9.7. ADVERSE EVENT REPORTING

Adverse event reporting requirements will be based on the time period in which the adverse event occurs. It is understood that many of the signs and symptoms observed with ICU patients are expected. However, these should still be reported as adverse events if they meet the definitions of the Protocol. A “clinical care” event should therefore be reported as an adverse event if it meets any of the definitions. A group of symptoms that can be combined under one diagnosis, should be reported as a single adverse event. If a group of symptoms cannot be combined under one diagnosis, the symptoms should be reported as separate adverse events. These events will be reported as the number of events per time of exposure to the device.

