6.4 STUDY OBSERVATION PERIOD

The Study Observation Period begins when the patient starts treatment and will continue up to a maximum of 168 hours from the time of Observation Start. **Patient will begin the Observation Period before the patient has reached 12 hours on CRRT.** A patient may begin CRRT therapy and SCD treatment at the same time, which would also mark the beginning of the Study Observation Period.

This observation period has been broken into seven 24 hour time periods. It ends when the patient has reached 168 hours in the observation period or when the patient meets the termination criteria outlined in **Section 7.2** as determined by the Principal Investigator or Medical Team at the participating Clinical Site.

All tests are scheduled on a 24 hour cycle, or once a day, and can be scheduled to be drawn around each participating site's ICU blood drawing schedule, with the exception of any test that requires a specific draw frequency.

The following information will be obtained for patients enrolled during the study observation period on a daily basis unless otherwise specified:

- **Vital Signs/Physical Assessment**
 - Temperature
 - Blood Pressure , heart rate
 - Urine Output (previous 24 hours)
 - Net Fluid Balance (previous 24 hours)
- **Clinical Laboratory Tests**
 - CBC with differential – every 12 hours (+/- 4 hours)
 - BUN, Creatinine
 - Na, K, Cl, HCO₃, Ca, ionized Ca, Mg, PO₄
 - ALT, AST, Bilirubin, ALP, Total Protein, Albumin, Glucose
 - PT, PTT, INR
- **Respiratory**
 - Status – Ventilator support (yes/no; date of extubation)
 - If on Vent: FiO₂
 - If on Vent with an arterial line: Arterial Blood Gas
 - If on Vent without an arterial line: Arterial Blood Gas (if available)
- **Blood for Research**
 - Collect at hours 48, 96, 144, and end of study (+/- 4 hours). If study observation period ends prior to hour 168, collect at end of study observation period. Blood for biomarkers will be collected as close as possible to the time of SCD scheduled changes in the days required (+/- 4 hours) if practical.
 - Blood sample will be sent to an outside laboratory for testing of biomarkers

- **CRRT Parameters (Start at hour 0)**
 - Parameters include modality, blood flow rate, net fluid removal, dialysate or replacement solution flow rate, citrate infusion rate, calcium replacement rate.
 - System performance (circuit survival - event driven)
 - Post filter ionized calcium (+/- 1 hour)

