6.5 STUDY FOLLOW UP PERIOD

6.5.1 POST END OF STUDY TREATMENT PERIOD

This Study Follow Up period has been broken into five 24 hour time periods. It starts when the patient has reached 168 hours in the observation period or when the patient meets the termination criteria outlined in **Section 7.2**. It ends at 120 hours or ICU discharge, whichever comes first. Record the following data daily in the Study Follow-up Period unless otherwise noted:

- **Vital Signs/Physical Assessment**
 - Blood pressure, heart rate, temperature
 - Physical Exam (first 24 hours only)
 - Urine Output (from previous 24 hours)
 - Net fluid balance (from previous 24 hours)
- **Clinical Laboratory Tests (first 24 hours only)**
 - CBC with differential
 - BUN, Creatinine
 - Na, K, Cl, HCO₃, Ca, Mg, Ionized Ca, PO₄

- **Respiratory**
 - Status – Ventilator support (yes/no)
 - If on Vent: FiO₂
 - If on Vent with an arterial line: Arterial Blood Gas(first 24 hours only)
 - If on Vent without an arterial line: Arterial Blood Gas (if available, first 24 hours only)
- **Renal Replacement Therapy status**
 - RRT status
- **Other (Event Driven)**
 - Microbiology/culture data
 - Adverse Events
 - Acknowledgement (yes/no) to antibacterial agents administered to the patient.

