7. TREATMENT INTERRUPTIONS – DISCONTINUATION CRITERIA

7.1. TREATMENT INTERRUPTION CRITERIA

The SCD is to be used continuously along with CRRT and changed every 24 hours and at any time the circuit exhibits significant clotting that impairs the functionality of the circuit.

In the event that a procedure is needed (e.g. CT-Scan, MRI), SCD treatment may be interrupted for a maximum of 12 hours (cumulative) per 24 hour period for these indications. In the event a patient needs to initiate ECMO in the middle of the SCD course, SCD treatment may be interrupted for up to 24 consecutive hours. Cumulative interruption of greater than 12 hours (or 24 hours for ECMO) will trigger the end of Observation Period and immediate initiation of the Follow-up period. These patients will not be removed from the study unless consent is withdrawn.

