7.2. TREATMENT DISCONTINUATION CRITERIA

Patients may be withdrawn from therapy prior to hour 168 for a variety of reasons. When therapy is discontinued prior to hour 168, the follow-up period will immediately begin and data will continue to be collected per protocol.

The Principal Investigator will assign a primary reason for therapy termination utilizing the categories listed in 7.3 and 7.4 below, and if appropriate, one or more subcategories.

7.3. CLINICAL CRITERIA:

1. Improvement in Clinical Status

If a patient's condition improves (e.g. renal condition has improved to the extent that CRRT can be discontinued or hemodynamic status has improved so that the dialysis modality can be changed from CRRT to IHD) treatment may be discontinued before the 168 hour treatment period. The decision to discontinue treatment based upon improvement in clinical status will be made by the Principal Investigator.

2. CRRT related medical events

Such as persistent leukopenia, neutropenia or thrombocytopenia based upon PI's clinical assessment.

3. SCD related medical events

Such as persistent leukopenia, neutropenia or thrombocytopenia based upon PI's clinical assessment of relationship to SCD.

4. CRRT Failure/Malfunction

Failure of the CRRT device and/or circuit, including inability to maintain vascular access that requires treatment to be discontinued prior to hour 168 of therapy.

5. SCD Failure/Malfunction

Any failure of the SCD █ that requires treatment to be discontinued prior to hour 168 of therapy e.g. clotting or evidence of leakage in the SCD █ or inability to maintain a patent circuit.

6. Death**7. Withdrawal of life support****8. Concomitant Medical Conditions**

Need for medical, surgical or diagnostic procedures that necessitate discontinuation of SCD treatment for longer than the allowable 12 hours per 24 hour period.

9. Regional Citrate Anticoagulation Intolerance

All patients must be able to tolerate and achieve satisfactory regional citrate anticoagulation. Tolerance of regional citrate anticoagulation is defined as achieving:

- Two (2) consecutive circuit ionized calcium levels of < 0.40 mmol/L (or < 1.6 mg/dL),
- At least 30 minutes apart, and
- Within the first 12 hours of CRRT initiation.

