9.7.2. ENROLLMENT PERIOD THROUGH END OF STUDY

All adverse events that occur from the time of enrollment will be recorded as follows:

- Serious Adverse Events (identified in **Section 9.2**) will be recorded until Day 60 after enrollment, death, or patient withdrawal of study consent, whichever occurs first.
- Non-serious adverse events will be recorded until end of study follow-up period after enrollment, death, patient withdrawal of study consent or until hospital discharge, whichever occurs first.

Any serious adverse event (regardless of relationship to the treatment) occurring from the time of enrollment through end of study must be reported to CytoPherx Inc, or designee, within 24 hours of knowledge of the event.

Each clinical trial site will be supplied with written SAE reporting

instructions, SAE reporting forms and contact information for reporting of serious adverse events.

For any AE that is ongoing at the time of the initial report, periodic follow-up information will be required until the adverse event is resolved or the patient is no longer in the study, whichever occurs first.

The Investigator is responsible for all adverse events reporting to the Institutional Review Board (IRB) according to the requirements of the IRB and for providing clinical trial monitors with all medical records needed to source-verify the adverse events.

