Besides the test of the hypothesis the study is focused on observable, empirical and laboratory determinations of patient safety while on the SCD. Previous human trials have been conducted on the SCD device and the protocol contains a review of AE and SAE data from all SCD human studies and findings from those studies contributed to constructing the investigative safety profile. Safety endpoint measures specified in the protocol include adverse events, laboratory safety parameters, vital signs, ventilation status and hemodynamic variables. Device integrity and performance measurements are also defined as are circumstances which demand premature termination of SCD treatment.

Prolonged exposure to the SCD is anticipated to result in superior outcomes, although as noted above, this pilot study is not designed to assess for efficacy. However, we understand that a minimum amount of exposure to the SCD will be required for an appropriate safety analysis and for making any inference regarding efficacy. The ppCRRT experience demonstrated that the majority of patients (201/370) received CRRT for 1 to 7 days and exhibited 65% survival (Symons et al CJASN 2007 Table7). Assuming our trial includes patients with similar illness severity, we have established a 72 minimum number of hours a patient will be treated with the SCD to be included in the final outcome analysis.

This trial is an early safety efficacy study but is not powered for statistical significance. Insights into a comparison of historical controls matched to SCD treated patients will utilize the ppCRRT Registry to match for: etiology of AKI, co-morbidities, CRRT modality, dose and form of anticoagulant, adverse events. [10].

The ppCRRT Registry has data fields for the primary reason for CRRT, including AKI and its cause, as well as co-morbidities which will be matched for primary organ system involvement. The CRRT modality was evenly distributed between convective and diffusive modality, with 60% of the convective modalities provided as CVVH and 40% as CVVHDF. The anticoagulant protocol will be standardized with ACD-A/CaCl₂ and all centers used the same protocol in ppCRRT Registry as outlined in this study protocol. Thus, the ppCRRT Registry dataset will be able to be matched to our study patient cohort. Also as noted above, patients will be matched for age, size and PRISM II score.

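### The only stated adverse event rate divides by device time, but events are recorded well beyond device time and no on-device window is defined

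*Combined protocol and SAP*

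**What the plan says.** Section 9.7 describes which events are reportable and closes with the only adverse event summary measure in the document: "These events will be reported as the number of events per time of exposure to the device".

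The recording windows are in Section 9.7.2. SAEs "will be recorded until Day 60 after enrollment, death, or patient withdrawal of study consent, whichever occurs first". For the rest, "Non-serious adverse events will be recorded until end of study follow-up period after enrollment, death, patient withdrawal of study consent or until hospital discharge", whichever comes first. Section 6.5.1 limits that follow-up period: "It ends at 120 hours or ICU discharge, whichever comes first". Recording starts at enrollment, so events before the first SCD treatment are captured too (Section 6.3).

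Device time is much shorter. The observation period starts with treatment and "will continue up to a maximum of 168 hours from the time of Observation Start". It can be shorter still. Under Section 7.1, "SCD treatment may be interrupted for a maximum of 12 hours (cumulative) per 24 hour period for these indications". Under Section 7.3, item 1, if the patient improves, "treatment may be discontinued before the 168 hour treatment period".

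Appendix D lists adverse events under patient safety without naming a statistic, and Section 11 promises only basic statistics. No section defines a treatment-emergent or on-device window.

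**The concern.** A rate is interpretable when the events in the numerator could only have arisen during the time in the denominator. Here most of the SAE recording window can add events but no exposure. The result would be neither an on-device rate nor a follow-up rate.

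The mismatch also varies between patients, because device time is tied to outcome. Improvement, death, SCD-related events and device failure all end treatment (Section 7.3). A patient who stops early has a small denominator and, if alive, nearly the same SAE window as everyone else. The rate then partly measures why treatment ended.

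Safety is the primary objective, and adverse events are the first safety measure listed in Section 3.2. With up to 30 patients, a few with short exposure can move a pooled rate. A rate per device time also has no counterpart in historical CRRT patients, who have no SCD time.

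**Working it through.** The plan states no adverse event rate, expected count or safety threshold, so there is no figure to reproduce. The check compares the recording window with device time.

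**Inputs from the protocol**
- Maximum device time: 168 h / 24 = 7 days (Section 6.4).
- SAE window: 60 days (Section 9.7.2).
- Non-serious window: device time plus at most 120 h / 24 = 5 days (Sections 6.5.1 and 9.7.2).
- A 3-day example, from the 72-hour minimum for the final outcome analysis (Section 11).
- Mortality scenarios: 31.4% at day 60 in the earlier US pilot (Section 2.4.1); 35%, from 65% survival in the registry (Section 11); 50% (synopsis rationale).

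**Assumptions, not in the protocol:** the off-device event rate as a fraction f of the on-device rate, and the mean day of death d.

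**Formula.** With T device days and a recording window of W days, the reported rate divided by the true on-device daily rate is

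R = [T + (W − T) × f] / T, which is W / T when f = 1.

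**Step 1. Constant rate (f = 1), alive at day 60**

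| Device days T | SAEs, 60/T | Non-serious, at most (T + 5)/T |
|---|---|---|
| 7 | 8.57 | 12/7 = 1.71 |
| 5 | 12.0 | 10/5 = 2.00 |
| 3 | 20.0 | 8/3 = 2.67 |

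The maximum permitted interruption, 12 h in every 24 h, would leave 7 × 0.5 = 3.5 device days, and 60/3.5 = 17.1 for SAEs.

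**Step 2. SAEs clustered on treatment (f < 1), alive at day 60**

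| f | T = 7 | T = 3 |
|---|---|---|
| 0.50 | (7 + 53 × 0.50)/7 = 4.79 | (3 + 57 × 0.50)/3 = 10.5 |
| 0.25 | (7 + 53 × 0.25)/7 = 2.89 | (3 + 57 × 0.25)/3 = 5.75 |
| 0.10 | 1.76 | 2.90 |
| 0 | 1.00 | 1.00 |

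**Step 3. Deaths, f = 1, 7 device days.** Mean follow-up = (1 − m) × 60 + m × d, divided by 7.

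| Mortality m | d = 10 | d = 30 |
|---|---|---|
| 31.4% | 44.3/7 = 6.33 | 50.6/7 = 7.23 |
| 35% | 42.5/7 = 6.07 | 49.5/7 = 7.07 |
| 50% | 35.0/7 = 5.00 | 45.0/7 = 6.43 |

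**Step 4. Dependence on treatment length.** Take an illustrative 0.02 SAEs per day in two patients followed for 60 days: 0.02 × 60 = 1.2 expected SAEs each. The reported rate is 1.2/7 = 0.171 per device-day after 7 days of SCD and 1.2/3 = 0.400 after 3 days. That is a 7/3 = 2.33-fold difference with identical risk.

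**Step 5. After matching the windows.** On-device events over device time, or all events over follow-up time, gives a ratio of 1.0 by construction.

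**The case against.** The strongest reply is that Section 9.7 never says post-device events are counted. It opens by tying reporting requirements to the period in which an event occurs, and a rate per exposure time can be read as events during exposure. Events are scheduled separately for treatment, follow-up and days 28 and 60 (Appendices F to H), and the DSMB is to look at timing using display specifications set in advance (Section 10). That reading is possible, but it is not written down. The sentence refers to all reportable events, and the DSMB specifications are not in the document, so they cannot settle it. If on-device events were meant, the text needs to say so.

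The size is also open to challenge, and much of that challenge stands. A constant SAE rate from multi-organ failure through recovery is unlikely, and deaths shorten follow-up. Only SAEs run to day 60. In the earlier US pilot 28 of 199 events were serious (Table 3). Borrowing that mix, although that study's recording windows are not given, the inflation for all events together at 7 device days and constant rates is 199 / (28 × 7/60 + 171 × 7/12) = 199/103.0 = 1.9.

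The 72-hour rule may remove the shortest exposures: "we have established a 72 minimum number of hours a patient will be treated with the SCD to be included in the final outcome analysis". Whether it applies to adverse event rates is unclear, so the examples above stop at 3 days.

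Finally, this is a single-arm pilot without statistical power, no stated decision rests on this rate, and the planned historical comparisons concern mortality and dialysis dependency. Section 11 names adverse events only among the items for matching to the registry. These points limit the consequences but leave the mismatch in place.

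**Conclusion.** The point holds: as written, the only stated adverse event rate under the primary safety objective mixes off-device events with on-device time and varies with treatment length. For SAEs in a day-60 survivor at a constant rate, the factor is 8.6 at 7 device days and 20 at 3. For non-serious events it is at most 1.7 and 2.7. It falls to about 5 to 7 under the mortality scenarios at 7 device days, to 2.9 if the off-device SAE rate is a quarter of the on-device rate, and to 1.0 if no SAE occurs off device. The event-rate fractions and mean days of death are assumptions.

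A reader might infer more than the document supports:
- *That 8.6 is a minimum.* It is not. Shorter device time raises the factor, but deaths and events clustered on treatment lower it.
- *That all adverse events are inflated this much.* Non-serious recording stops at most 5 days after treatment.
- *That a primary safety result is invalid.* Safety is the primary objective, but no single primary safety statistic, threshold or test is defined.
- *That the plan expressly commits to counting events to day 60 in this rate.* That is the natural joint reading of Sections 9.7 and 9.7.2. Strictly, the numerator window is undefined.

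**What to change.** Replace the closing sentence of Section 9.7 so that numerator and denominator cover the same period:

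1. Events with onset during SCD treatment, plus a lag that the sponsor pre-specifies, per SCD-day.
2. Events outside that window, per patient-day of follow-up: to day 60 or death for SAEs, and to the end of the follow-up period for non-serious events.
3. Number and percent of patients with at least one event in each period.

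If adverse events are set against historical data, use patient-days or percent of patients, because controls have no SCD time.

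The cost is one paragraph of analysis text and slightly more tabulation. Event onset dates must be captured on the case report form; the day 28 and day 60 schedule (Appendix H) asks only for SAEs since the last visit, so this should be confirmed.
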